## HMC RESEARCH PROTOCOL

Additionally, its mechanism of action involves the formation of a protective barrier over the wound site, potentially reducing infection risk and facilitating a controlled healing process (8).

While some studies have explored the application of Hemagel Ointment in wound healing, its specific effects on post-episiotomy and CS scars remain relatively uncharted territory. Consequently, there exists a compelling need to conduct well-designed clinical trials that rigorously assess Hemagel Ointment's efficacy and safety in the context of these surgical procedures.

Therefore, the aim of this study is to evaluate the effectiveness and safety of Hemagel Ointment in post-episiotomy and cesarean section scar care through a randomized clinical trial. This trial will provide comprehensive evidence regarding the effectiveness of Hemagel Ointment in promoting wound healing, alleviating pain, improving scar appearance, and enhancing patient satisfaction in these specific contexts.

By conducting a rigorous randomized clinical trial, we seek to generate high-quality data that will inform clinical practice and guide healthcare professionals in selecting optimal interventions for scar management in post-episiotomy and cesarean section cases. This research will contribute to the existing body of knowledge in scar care and provide valuable insights for healthcare professionals, ultimately improving patient outcomes.

The results of this study have the potential to facilitate evidence-based decision-making, facilitate personalized patient care, and potentially reduce the burden of complications associated with post-episiotomy and cesarean section scars. Furthermore, the findings will contribute to advancing the field of scar management and may pave the way for future research and the development of targeted interventions.

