#### **Blinding:**

We will be blinding the tube ointments to ensure impartiality in the assessment of efficacy between the two treatments. This adjustment will enable us to minimize potential biases and ensure the integrity of our results.

The ointment tubes will be packaged in identical outer packaging, such as opaque boxes, to conceal any distinguishing features.

This approach will ensure that the participants nor the assessors of wound know which

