**Here are some potential anticipated risks to consider:**

- Allergic reactions: Some participants may experience allergic reactions to the topical treatments, HM Gel, or BS Ointment. Allergic reactions can range from mild skin irritation to more severe symptoms, such as rash, itching, or swelling.
- Skin irritation: As with any topical treatment, there is a possibility of skin irritation at the application site. Participants may experience redness, itching, or discomfort around the wound area.
- Delayed wound healing: There is a small possibility that the application of the treatments may interfere with the natural wound healing process, leading to delayed wound closure or complications in some participants.
- Unsatisfactory scar appearance: Despite the use of the treatments, some participants may not achieve the desired cosmetic outcomes in scar appearance. This could potentially impact patient satisfaction with the treatment.
- No treatment effect: It's possible that neither treatment (HM Gel or BS Ointment) may demonstrate a significant effect on wound healing or scar management, leading to no substantial improvement in the participants' conditions.

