### Subject Withdrawal/ Withdrawal of Consent

In this study, participants have the right to withdraw from the trial at any time without providing a reason. Withdrawal of consent will not affect their current or future medical care. Participants who decide to withdraw from the study will be informed that they are free to do so without any negative consequences. Their decision to withdraw will be respected, and their data collected up to the point of withdrawal will be retained and included in the analysis, unless they specifically request their data to be removed.

To ensure proper handling of participant withdrawal, the study team will clearly communicate the withdrawal process during the informed consent process. Participants will be provided with contact information for the study coordinator or principal investigator, who will be available to answer any questions or concerns related to the study or the withdrawal process.

If a participant decides to withdraw their consent, their study participation will be terminated immediately. Any unused investigational product (HM Gel or BS Ointment)will be collected, and no further assessments or interventions will be performed on the participant.

The reasons for withdrawal, if provided voluntarily by the participant, will be recordedto inform the study team of potential issues and ensure continuous improvement of the research process.

Participant confidentiality will be strictly maintained throughout the study and beyond. All data obtained from participants who withdraw their consent will be handled withthe utmost confidentiality and will not be disclosed in any study-related publications or presentations.

It is important to emphasize that participant withdrawal is entirely voluntary, and participants will be assured that their decision will not impact their relationship with the

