### 10. Statistical Consideration and Data Analysis :

#### Randomization and Allocation Concealment:

We will be blinding the tube ointments to ensure impartiality in the assessment of efficacy between the two treatments. This adjustment will enable us to minimize potential biases and ensure the integrity of our results.

The ointment tubes will be packaged in identical outer packaging, such as opaque boxes, to conceal any distinguishing features.

This approach will ensure that the participants nor the assessors of wound know which ointment is being used. Blinding of data analysts will help ensure impartiality during the analysis process.

Randomization: We will indeed use computer-generated random numbers or randomization software to ensure unbiased and unpredictable allocation. Instead of stratifying during randomization, we will collect comprehensive data on age group, BMI, and type of surgery. Subgroup analyses will be conducted during data analysis, allowing for a thorough examination of treatment effects within specific subgroups.

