## HMC RESEARCH PROTOCOL

### 11. Adverse Event Reporting

#### Monitoring and Reporting of Adverse Events:

We will implement a systematic monitoring and reporting process to promptly identify and assess adverse events throughout the study. The following steps will be followed:

-Participant Education: Participants will be provided with clear instructions on how to recognize and report any potential adverse events they may experience during the study. They will be informed about the importance of timely reporting and the methods for contacting the study team.

-Documentation: All adverse events reported by the participants or observed by the study personnel will be documented in detail. This documentation will include the nature of the event, date and time of occurrence, severity, duration, related symptoms, and any actions taken.

-Classification and Severity Assessment: Adverse events will be classified and assessed for severity according to predefined criteria. The severity levels may include mild, moderate, or severe, based on the impact on the participant's well-being and the need for medical intervention.

-Causality Assessment: Adverse events will be evaluated for their potential relationship to the investigational product (Hemagel Ointment) or other study procedures. Causality assessments will consider factors such as temporal association, known side effects of the product, and the presence of alternative explanations.

-Reporting and Follow-up: Adverse events of moderate to severe intensity or those considered related to the investigational product will be promptly reported to the principal investigator and the relevant ethics committee or institutional review board (IRB). The reporting will include a comprehensive description of the event, its severity, the participant's characteristics, and any actions taken or planned.

We will ensure that the reporting timelines align with the revised version of IRB SOP 09, available on the Abhath download center. Specifically, Serious Adverse Events (SAE) will be reported within 7 days, and any other unanticipated problems will be reported within 14 days.

We are committed to ensuring the highest standards of participant safety and ethical conduct throughout the study.

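### The adverse-event causality rule names Hemagel alone, so a mild reaction to the control ointment has no 'related' category, and the stated safety aim has no by-arm summary

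*Combined protocol and SAP*

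**What the plan says.** Section 11 (Adverse Event Reporting) contains two linked rules.

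- Causality: each event is evaluated for its "relationship to the investigational product (Hemagel Ointment) or other study procedures". The considerations listed are timing, the product's recognised side effects and other possible explanations.
- Reporting to the principal investigator and the ethics committee or IRB: "Adverse events of moderate to severe intensity or those considered related to the investigational product will be promptly reported".

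The same section records all events that participants report or staff observe. It sets 7 days for serious adverse events and 14 days for other unanticipated problems, and neither limit names a product.

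Elsewhere the protocol uses a wider definition. Under Subject Withdrawal/ Withdrawal of Consent: "Any unused investigational product (HM Gel or BS Ointment)will be collected". Under Section 9 (Risk): "Some participants may experience allergic reactions to the topical treatments, HM Gel, or BS Ointment".

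On masking, the Blinding paragraph of Section 7 says: "The ointment tubes will be packaged in identical outer packaging, such as opaque boxes, to conceal any distinguishing features". Section 10 concludes: "This approach will ensure that the participants nor the assessors of wound know which ointment is being used". Data analysts are also to be blinded. Whoever judges causality is not identified.

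On purpose, Section 3 states that "the aim of this study is to evaluate the effectiveness and safety of Hemagel Ointment". Section 4 and the Outcomes section place the reduction of complications in the primary objective and the primary outcome. The Statistical Analysis Plan in Section 10 describes no analysis of adverse events, related events or complications.

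**The concern.** The term 'investigational product' has two meanings in one protocol, and the narrower one sits where it has a consequence. For a topical product, mild local reactions are among the harms to be expected, and the risk section lists allergic reactions and skin irritation for these treatments. For a mild event, being judged related is what triggers prompt reporting. A causality question that names one of the two products leaves the control arm without a matching category.

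Three things are at stake. Women in the control arm should have the same reporting route as women in the gel arm. A count of related events by arm can be interpreted only if both arms face the same question. And a trial that puts safety in its aim needs a planned way to summarise it, which Section 10 does not supply.

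**Working it through.** **Step 1. Set the definitions side by side.**

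| Place in the protocol | Products covered |
|---|---|
| Section 11, causality | Hemagel only, plus study procedures |
| Section 11, reporting | Investigational product, not named |
| Subject Withdrawal | HM Gel or BS Ointment |
| Section 9 (Risk), allergic reactions | HM Gel or BS Ointment |

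The causality wording does not fit the other places. The reporting sentence takes its meaning from whichever definition the reader carries into it.

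**Step 2. Follow each kind of event through Section 11, read literally.**

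| Event | Recorded | Prompt report to investigator and IRB |
|---|---|---|
| Mild, caused by HM Gel | Yes | Yes, as related |
| Mild, caused by BS Ointment | Yes | Not as related; no such category |
| Moderate or severe, either arm | Yes | Yes, by severity |
| Serious, either arm | Yes | Yes, within 7 days |

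The gap is the second row. The 14-day route for unanticipated problems is not a dependable substitute, because Section 9 lists allergic reactions and skin irritation among the anticipated risks.

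**Step 3. Ask what a masked rater would do.** A rater who does not know the product puts the same Hemagel question to every woman. If the two products' reactions look alike, the related counts are affected equally in both arms. A control-arm reaction may then be labelled as related to a product the woman never used, but it is still reported. Attribution differs by arm only if some BS reactions are marked unrelated, which can happen in two ways:

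- The rater recognises the product. This is possible: the rater is not named, and only the outer packaging is described as identical. The products are a gel and an ointment, and Section 3 says beta-sitosterol is in common use at this hospital.
- The rater, though masked, judges against Hemagel's known side effects alone, and a BS reaction does not resemble them.

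The documents establish neither.

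**Step 4. Size under stated assumptions.** The plan gives no adverse-event rate, so there is no figure of its own to reproduce.

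- n = 120 per arm: about 60 per group (Section 6, Sample Size Adjustment) × 2 surgery types.
- r = true rate of product reactions, equal in both arms (assumed: 5%, 10%, 15%).
- u = share of BS reactions marked unrelated for either reason above (assumed: 0, 25%, 50%).
- Expected related events: HM Gel = n × r; BS Ointment = n × r × (1 − u).

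| r | u = 0 | u = 25% | u = 50% |
|---|---|---|---|
| 5% | 6 v 6 | 6 v 4.5 | 6 v 3 |
| 10% | 12 v 12 | 12 v 9 | 12 v 6 |
| 15% | 18 v 18 | 18 v 13.5 | 18 v 9 |

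For example, at r = 10% and u = 50%: 120 × 0.10 = 12, and 12 × 0.50 = 6. With u = 0 the wording creates no imbalance at any rate. Any imbalance comes from u, about which the documents say nothing.

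**The case against.** The strongest reply is that this is loose drafting with little effect. The reporting sentence does not repeat the Hemagel parenthesis, so read with the withdrawal section it can cover both products. Section 3 presents beta-sitosterol as usual practice, which may explain why only Hemagel is named. The relatedness clause governs notification, not what enters the dataset: all events are recorded with severity and duration and followed to resolution or stabilisation. Moderate, severe and serious events do not depend on it.

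Most of this stands, and it limits the point to mild events and to one of two available readings. It does not remove the point, because a protocol should not leave that choice to the person completing the form. Nor does the mention of study procedures help. Section 6 separates interventions from procedures, and the reporting trigger refers to the investigational product only.

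A reader might go further and infer that related events are therefore counted unequally and that the safety comparison is biased, for instance 6 v 0 at a 5% rate in both arms. The documents do not support that. It would require every control-arm reaction to be marked unrelated, while the plan says participants and wound assessors are masked. An all-events comparison would be untouched, and no between-arm test of related events is planned for such a bias to distort.

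**Conclusion.** The inconsistency is real and is established from the text alone. Section 11 judges causality against Hemagel only, while the protocol elsewhere treats both products as investigational and expects reactions to either. Its definite consequence is narrow: read literally, mild BS Ointment reactions have no related category and can miss the report that the same reaction to HM Gel would receive.

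Unequal attribution between arms is a conditional risk. It depends on failed masking of an unnamed rater, or on judging only against Hemagel's side-effect profile. The counts above rest on assumed rates and shares and on pooling both surgery types; they show the mechanism and do not predict the trial's results.

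Separately, and whatever the state of masking, the analysis plan has no by-arm summary of adverse events or complications, although safety is in the aim and complications are in the primary objective and outcome. No figure in the plan is affected. The change is worth making because it costs almost nothing.

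**What to change.** 1. In Section 11, reconcile the causality item with the risk and withdrawal sections by defining it as relationship to the assigned study product (HM Gel or BS Ointment), judged blind to allocation. Use the same term in the reporting sentence so that one rule applies to both arms.
2. In Section 11, name the role that judges causality and state that this role is masked.
3. In Section 10, add a table by arm giving the number and percentage of women with any adverse event, any product-related event and any wound complication, each with a risk difference and 95% confidence interval.

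The cost is a wording change, one table and a few more mild control-arm reports. Sample size, visits and the planned efficacy analyses do not change.

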## HMC RESEARCH PROTOCOL

- Follow-up and Documentation: Adverse events will be closely monitored and followed up until resolution or stabilization. The progress and outcomes of the adverse events, including any necessary medical interventions or treatments, will be documented in the participant's records.

### 12. Ethical Consideration

The study will only be conducted after review and approval from MRC.

The study will be conducted in full conformance with principles of the “Declaration of Helsinki”, Good Clinical Practice (GCP) and within the laws and regulations of MoPHin Qatar.”

### 13. Sponsor, Funding & Collaborator Information

Not applicable

### 14. Dissemination of Results and Publication policy

Once the study is completed it will be sent for publication after review by the Medical Research center. We also plan to present the results of the study in various international conferences.

### Appendices

*Data collection sheet Questionnere/Survey and Research consent form.*
